5.4.7. Transcranial Doppler (Parts B and C)

TCD results from the 3 years prior to signing ICF, if available, will be recorded as part of the Medical history for participants in Part C.

TCD TAMM blood flow velocity is also being obtained (in accordance with the TCD reference manual) as an assessment to determine treatment effect (refer to [Section 5.5](#) and [Appendix 3](#) and [Appendix 5](#)); however, abnormal values can indicate a safety concern and will be followed up as appropriate. Specifically, standard clinical practice for primary stroke prevention will be followed (eg, any TCD values \geq 200 cm/sec by nonimaging TCD or \geq 185 cm/sec by TCDi will require repeat TCD within 4 weeks. In the case of a second TCD value \geq 200 cm/sec by nonimaging TCD or \geq 185 cm/sec by TCDi, the site Investigator may offer the participant treatment with a stroke prevention protocol utilizing prophylactic transfusion as per standard clinical care if in place at that site's hospital or clinic).

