10.3.4. Handling of Missing Data

Missing data will not be imputed. The details on efficacy analysis for participants that have been transfused will be detailed in the Statistical Analysis Plan.

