### **8.2.1. Analysis of the Primary Efficacy Endpoint**

Change from baseline in hemoglobin to Week 24 will be summarized descriptively. The changes from baseline will be presented including the (absolute) values at each visit. Additionally, a responder endpoint defined as an increase in Hb >1 g/dL compared to Baseline, will be summarized descriptively at Week 12 through Week 24. No imputation will be performed for this endpoint.

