## **6. ANALYSIS POPULATIONS**

### **6.1. Efficacy Evaluable Population**

All subjects who received at least one dose of study drug will be included in the Efficacy Evaluable population (EE). The EE population will be the primary population for the efficacy analyses.

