## 7.2. Efficacy Analysis

Efficacy data will be summarized using the EE population.

The primary endpoint for Part C is change from baseline to 48 weeks in cerebral blood flow as measured by the TAMM TCD velocity.

TCD flow velocity will be summarized descriptively at Week 24 and Week 48 for observed values and absolute changes. TCD is presented as TCD (non-imaging) in the summary table. TCDi (imaging) has been normalized to TCD (non-imaging) by adding 15 cm/sec.

The proportion of subjects with normal TCD flow velocity (< 170 cm/sec by nonimaging TCD or < 155 cm/sec by TCDi) at 48 weeks will be summarized descriptively for the overall population and by Baseline TCD category (Normal, Conditional).

Hb response, defined as an increase in Hb > 1 g/dL, will be summarized descriptively at Week 24 and Week 48. Subjects who drop-out early or do not have a Week 24 or Week 48 visit, are not included in the analysis for Hb response at each of the respective visits. Additional response assessment at each visit will be summarized descriptively. No missing data imputation or adjustment for RBC transfusion will be performed for this endpoint.

Additionally, Hb response at Week 24 and Week 48 will be summarized using the treated population. All subjects treated will be included in the denominator for Hb response.

For subjects who have had a Hb response at least 1 visit, the time to the first response will be summarized descriptively.

Hematology parameters (hemoglobin, reticulocyte count, indirect bilirubin, and LDH) and in addition to each visit for observed values and changes (absolute and percent) from baseline using appropriate descriptive statistics. If indirect bilirubin is missing and direct and total bilirubin are collected, indirect can be calculated as:

$$\text{Indirect Bilirubin} = \text{Total Bilirubin} - \text{Direct Bilirubin}.$$

To evaluate the effect of voxelotor on the incidence of stroke and vaso-occlusive crisis (VOC), the annualized incidence rate will be summarized and 95% CI provided.

Efficacy assessment will be summarized by subgroups defined by subjects' sex, baseline HU use, and 4-11 age group (4 to 7 years and 8 to 11 years). Efficacy assessments to be summarized by subgroup include Hb response and change from baseline for hematology parameters and TCD flow velocity.

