## 8.2. Efficacy Analysis

All efficacy data will be summarized using the EE population.

Hematology and hemolysis parameters (hemoglobin, reticulocyte count, indirect bilirubin, and LDH) will be summarized at Week 24 and Week 48 in addition to each visit for observed values and changes (absolute and percent, as appropriate) from baseline using appropriate descriptive statistics. If indirect bilirubin is missing and direct and total bilirubin are collected, indirect can be calculated as:

$$\text{Indirect Bilirubin} = \text{Total Bilirubin} - \text{Direct Bilirubin}.$$

Hb response, defined as an increase in Hb  $> 1$  g/dL, will be summarized descriptively at Week 24 and Week 48 with 95% confidence intervals provided for the response rates. Subjects who drop-out early or do not have a Week 24 or Week 48 assessment, are not included in the analysis for Hb response. Additional response assessments at each visit will be summarized descriptively. No missing data imputation or adjustment for RBC transfusion will be performed for this endpoint.

Additionally, Hb response at Week 24 and Week 48 with 95% confidence intervals will be summarized using the treated population. All subjects treated will be included in the denominator for Hb response, and subjects without a Week 24 or Week 48 assessment will be counted as non-responders at each relevant timepoint.

For subjects who had a Hb response at least 1 visit, the time to the first response will be summarized descriptively (ie, median, first quartile, third quartile, and range).

The annualized incidence rates for VOC and stroke and the associated 95% CIs will be presented. Annualized rate is defined as the total number of events divided by total person years. Total person-years is defined as the sum of subject treatment period in years which covers the time from first dose to last dose. VOC is defined based on clinical review of adverse event MedDRA preferred terms (eg, sickle cell anemia with crisis, acute chest syndrome, and pneumonia).

Exploratory analysis for change from baseline to Weeks 24 and 48 in height, weight, and head circumference, will be summarized using continuous descriptive statistics at each visit.

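### Part D's Hb response rule, as worded, discards observed Week 24 values, and Part C's normal TCD at Week 48 has no stated rule for children without the reading

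*SAP*

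**What the plan says.** **Part C SAP, 6.1 and 7.2.** The efficacy population is every dosed child: "All subjects who received at least one dose of study drug will be included in the Efficacy Evaluable population (EE"), and "Efficacy data will be summarized using the EE population". Normal TCD (below 170 cm/sec, or below 155 cm/sec by TCDi) "at 48 weeks will be summarized descriptively for the overall population and by Baseline TCD category (Normal, Conditional"). No denominator or missing-visit rule follows. Hb response in the same section gets two versions. One leaves out children without the Week 24 or Week 48 visit, each at the visit concerned. The other uses the treated population: "All subjects treated will be included in the denominator for Hb response". TCD velocity is summarized at Weeks 24 and 48 only.

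**Part D SAP, 8.2.** The observed-case rule is "Subjects who drop-out early or do not have a Week 24 or Week 48 assessment, are not included in the analysis for Hb response", with no limit to the visit concerned. The next paragraph plans an all-treated rate with 95% confidence intervals, counting a missing Week 24 or Week 48 value as non-response at that timepoint.

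**Protocol.** Section 10.3.4: "Missing data will not be imputed". Section 6.2 keeps children who stop study drug in the study assessments, except after withdrawal of consent or loss to follow-up. Section 5.4.7 requires a repeat TCD after a value of at least 200 cm/sec (185 by TCDi); after a second such value, "the site Investigator may offer the participant treatment with a stroke prevention protocol utilizing prophylactic transfusion". Appendix 5 schedules a TCD at early termination.

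**Part A/B SAP, 8.2.1.** A supplementary Hb responder summary is described with "No imputation will be performed for this endpoint" and no stated denominator.

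**The concern.** A responder proportion depends on its denominator. Normal TCD at Week 48 is a protocol secondary endpoint and the only responder measure of TCD in Part C. With no imputation and no missing-visit rule, a programmer will probably divide by the children who have a Week 48 reading. This is a single-arm study, so there is no comparator to reveal a shift caused by who remained. Repeat and early-termination TCDs are collected but fall outside the Week 24 and Week 48 summaries, so a child's last reading before leaving may enter no planned summary.

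In Part D, the literal rule makes the observed-case Week 24 response rate a rate among children who stayed, while the Week 24 Hb change beside it uses everyone with a value.

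**Working it through.** **1. The plan's own figures.** No dropout, normal-TCD or Hb response rate is given. The only formal Part C figure is power for mean TCD change (Part C SAP 5.1): 30 children, 15 cm/sec, SD 22 cm/sec, paired t-test, two-sided alpha 0.10. The noncentrality is (15/22) × √30 = 3.73, and the noncentral t gives 97.7% power, consistent with the stated figure above 95%. It does not bear on a responder rate.

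**2. Normal TCD at Week 48.** Let N be treated, n observed at Week 48 and r normal among those observed. The observed-case rate is r/n. The all-treated rate with missing counted as not normal is r/N. The gap is

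r/n − r/N = (r/n) × (1 − n/N) = observed rate × missing share.

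N = 50 is the planned Part C size; the missing shares and observed rates are assumptions.

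| Missing | About 50% observed | Gap (points) | 80% observed | Gap (points) |
|---|---|---|---|---|
| 10% | 22/45 = 48.9% vs 22/50 = 44.0% | 4.9 | 36/45 = 80% vs 36/50 = 72% | 8 |
| 20% | 20/40 = 50% vs 20/50 = 40% | 10 | 32/40 = 80% vs 32/50 = 64% | 16 |
| 30% | 18/35 = 51.4% vs 18/50 = 36.0% | 15.4 | 28/35 = 80% vs 28/50 = 56% | 24 |

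With N = 70, the size under the potential modification, the gaps are nearly the same (for example 45/56 = 80.4% vs 45/70 = 64.3%). In a small baseline category a few children matter: if 8 were conditional at baseline, 2 lacked Week 48 and 4 of the other 6 were normal, the rates would be 4/6 = 67% and 4/8 = 50%.

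**3. Part D, Week 24 Hb response.** Assume 30 treated, all with a Week 24 Hb, 6 leaving before Week 48, and 12 of the 24 stayers responding at Week 24. The literal rule gives 12/24 = 50%. Keeping the 6 observed values gives:

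- 0 of 6 respond: 12/30 = 40%
- 1 of 6: 13/30 = 43%
- 3 of 6: 15/30 = 50%
- 6 of 6: 18/30 = 60%

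The discard can therefore raise, lower or leave the rate unchanged. In this example the all-treated rate equals the rate that keeps the 6, because nobody lacks Week 24.

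**4. Who is affected.** Under Protocol 6.2, stopping drug alone does not end assessments. The missing share consists of children who leave the study or miss the visit.

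**The case against.** The case for leaving the text alone has several sound parts.

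- **All-treated population.** A reader might infer that normal TCD and Part B Hb response are defined to exclude children without the visit. The documents do not say so. Both fall under an efficacy population of every dosed child; what is missing is the denominator and missing-visit rule. Population membership does not settle this, however: Part C Hb response is summarized in the same population and still needs a separate treated-population version.
- **Informative loss.** A reader might infer that children whose TCD worsens disappear before Week 48. Section 5.4.7 says only that prophylactic transfusion may be offered, not that the child leaves, and section 6.2 would keep a child who only stops drug in assessments. Such a child may have a Week 48 TCD affected by transfusion, which counting missing as not normal would not address. Selective loss is possible but not shown.
- **Visibility.** Disposition with reasons is planned, n is printed with the continuous TCD summary, and Protocol 10.3.3 has TCD listed at each visit. The size of the gap in data would be visible; a rate that accounts for it would not.
- **Part D.** The all-treated analysis keeps the Week 24 results of later leavers, so the harm is confined to the observed-case summary. The omission looks like a drafting slip relative to Part C.
- **Part B.** The responder rate is a supplementary descriptive summary, not a protocol endpoint.

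These points narrow the issue. They supply neither the missing TCD rule nor a correction to the Part D sentence.

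**Conclusion.** The point holds in a limited form. The Part D sentence, taken literally, removes observed Week 24 values of children who leave later; the direction is unknown and the all-treated analysis limits the effect. Normal TCD at Week 48 lacks a missing-visit rule and a treated-population companion. Its likely observed-case rate would exceed the all-treated rate by about 5 to 15 points at a 50% observed rate, or 8 to 24 points at 80%, if 10% to 30% lack the reading. Those shares and rates are assumptions, so the real size cannot be derived from the documents.

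It would go too far to say that the plan inflates its responder rates in general. Hb response in Parts C and D has a treated-population summary, the Part D effect has no fixed sign, and the gap in Part C measures sensitivity to missing readings, not demonstrated bias. No test or decision rule rests on these proportions, and the primary endpoints of Parts C and D (mean TCD change and adverse events) are separate analyses.

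**What to change.** 1. **Part D SAP 8.2:** limit the exclusion to the visit concerned, as the Part C sentence does, so that a child without an Hb value at a visit is left out of the observed-case rate at that visit only.
2. **Part C SAP 7.2, normal TCD:** state the observed-case denominator. Beside it, show the rate with all treated children in the denominator and no Week 48 TCD counted as not normal, overall and by baseline category.
3. **Part C SAP 7.2, TCD course:** tabulate children with a confirmed post-dose TCD of at least 200 cm/sec (185 by TCDi) at any reading, including unscheduled repeats and early-termination TCDs.
4. **Part C SAP 7.2, treated-population Hb response:** say that a missing visit counts as non-response, as Part D does.
5. **Part A/B SAP 8.2.1 (optional):** add an all-treated Hb responder row.

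The cost is SAP wording and a few table rows from data already scheduled for collection. The companion TCD rate is conservative and may misclassify a child with normal TCD who simply missed the visit, so it should accompany the observed-case rate and not replace it.

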Transcranial Doppler (TCD) ultrasonography can be used to assess cerebral blood flow and predict CNS events in SCD. TCD shows a higher mean intracranial arterial flow velocity in children with SCD (about 130 to 140 cm/sec) relative to those without SCD (about 90 cm/sec). The National Heart, Lung, and Blood Institute recommends chronic transfusion therapy for children with a TCD velocity exceeding 200 cm/sec based on the results of the STOP trial (Adams, 1998). TCD velocities of 170 to 200 cm/sec are designated as “conditional” and can progress into the abnormal range. Children in this category require close observation. Based on the results of the TWiTCH study, children on a chronic transfusion protocol for elevated TCD

velocity > 200 cm/sec for at least 12 months, can be safely transitioned to hydroxyurea (HU) (Ware, 2015).

Overall, the management strategies for SCD have evolved very slowly, and treatment of SCD remains a serious unmet medical need. In children, routine vaccination beginning in the 1970s contributed to the reduction in death rate as a result of infectious complication. Red blood cell (RBC) transfusions are administered to alleviate symptomatic anemia as well as for stroke treatment and prevention. Transfusions are costly, cumbersome, and not uniformly accessible and accompanied by risks, including iron overload (Wahl, 2009). HU therapy for SCD is limited by its side effect profile, poor patient adherence, variable patient responses, and concerns of long-term toxicity (Brandow, 2010). The only curative treatment is bone marrow transplantation from a histocompatible donor, an option that has been available since the 1990s (Platt, 2014), but bone marrow transplantation carries significant risks and is associated with a ~5% mortality rate (Nathan, 2013). Despite the current standard of care, including HU, blood transfusion, and palliative therapy for acute attacks, patients with SCD continue to suffer serious morbidity and premature mortality (Steinberg, 2003).

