5.4. Safety Assessments

5.4.1. Clinical Laboratory Studies

It is the responsibility of the Investigator to assess the clinical significance of all abnormal clinical laboratory values as defined by the list of normal values on file for the local clinical laboratory. All clinically significant laboratory value abnormalities are to be recorded as AEs.

For the purpose of this study, a clinically significant laboratory value will be any abnormal result that, in the judgment of the Investigator, is an unexpected or unexplained laboratory value or if medical intervention or corrective action (transfusion, hydration, initiation of antibiotics or other concomitant medication) is required. Any abnormal values that persist should be followed at the discretion of the Investigator.

Additional and repeat laboratory safety testing for the evaluation of abnormal results and/or AEs during the study may be performed at the discretion of the Investigator or upon request of the Sponsor. Repeat laboratory testing of abnormal potentially clinically significant or clinically significant results for the screening evaluation of the participant may be repeated once at the discretion of the Investigator.

All laboratory safety testing will be performed by the local laboratory.

Refer to [Appendix 1](#), [Appendix 3](#), [Appendix 5](#), and [Appendix 7](#), Schedule(s) of Study Assessments, for all time points.

The clinical laboratory tests that will be performed are listed in [Table 4](#) for Parts A, B, and C, and in [Table 5](#) for Part D.

Table 4: Parts A, B, and C: Clinical Laboratory Tests

Hematology	Serum Chemistry	Urine	Other

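### Parts C and D: a haemoglobin rise or normal TCD after transfusion counts in the drug's favour, and no planned companion analysis accounts for transfusion

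*SAP*

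**What the plan says.** Protocol 10.3.4 imputes nothing and adds: "The details on efficacy analysis for participants that have been transfused will be detailed in the Statistical Analysis Plan".

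The three SAPs then say the following.

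- **Part C SAP 7.2 and Part D SAP 8.2, Hb response (rise above 1 g/dL).** Both carry the same sentence: "No missing data imputation or adjustment for RBC transfusion will be performed for this endpoint". Each also plans a second Hb response summary with all treated subjects in the denominator. In Part D, "subjects without a Week 24 or Week 48 assessment will be counted as non-responders at each relevant timepoint".
- **Time to first Hb response.** Part C SAP 7.2: "For subjects who have had a Hb response at least 1 visit, the time to the first response will be summarized descriptively". Part D SAP 8.2 is similar. Transfusion is not mentioned.
- **TCD (Part C).** "TCD flow velocity will be summarized descriptively at Week 24 and Week 48 for observed values and absolute changes". The proportion with normal TCD at 48 weeks (below 170 cm/sec nonimaging, below 155 cm/sec imaging) is also descriptive. Transfusion is not mentioned for either.
- **Hb change and hemolysis markers (all parts).** Observed values and changes by visit, without mention of transfusion. For the Part B primary endpoint, Part A/B SAP 8.2.1 says: "Change from baseline in hemoglobin to Week 24 will be summarized descriptively". That SAP mentions transfusion only as a 12-month baseline history (8.1.3).

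The Part C and D SAPs record red-cell transfusions as concomitant medications (sections 4 and 5, Definitions). The efficacy population in each SAP is everyone who received study drug.

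**The concern.** Transfusion raises Hb directly, and it is used in response to the conditions this trial measures. The protocol foresees it during the study in two places. Section 5.4.1 calls an abnormal laboratory value clinically significant "if medical intervention or corrective action (transfusion, hydration, initiation of antibiotics or other concomitant medication) is required". Section 5.4.7 lets the investigator offer prophylactic transfusion after a second TCD at or above 200 cm/sec (185 by imaging). The second route starts from the Part C primary measurement itself. The limits on recent and chronic transfusion in section 4.2 apply only at entry.

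Parts C and D have no untreated group, so nothing in the data separates a transfusion effect from a voxelotor effect. If a child's Hb or TCD improves because of blood, the response and normal-TCD tables credit the drug. Part D also puts 95% confidence intervals around its response rates.

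**Working it through.** **The plan's own figures.** The paired-t power claims reproduce.
- Part C: N=30, difference 15, SD 22, two-sided alpha 0.10. Noncentrality is 15/22 × √30 = 3.73, and power is 97.7% (stated: above 95%).
- Part B: N=12, 0.8 and 0.6 g/dL, two-sided alpha 0.05. Noncentrality is 4.62, and power is 98.7% (stated: above 90%).

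Neither is in dispute. The SAPs plan no test, so no test result depends on transfusion.

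**Following the rules as written.**
1. Hb is scheduled at nine on-treatment visits in Parts C and D: Weeks 2, 4, 8, 12, 16, 20, 24, 36 and 48 (Protocol Appendices 5 and 7). A post-transfusion rise above 1 g/dL at any of them is a visit-level response, and the first such visit sets time to first response.
2. Part C TCD is scheduled at Screening, Week 24, Week 48 and early termination (Appendix 5). A child abnormal at Week 24 and on repeat may be offered transfusion. A Week 48 value below the threshold then counts as normal. The route therefore bears mainly on Week 48.
3. In the Part D treated-population summary, a child with no Week 24 or 48 value is a non-responder, but a transfused child with a sufficiently raised Hb is a responder. The Part C version likewise changes only the denominator.

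**Not every transfusion misclassifies (assumed values).** Baseline is 8.0 g/dL, Hb falls to 6.5, and the child is transfused. A later 9.2 gives 9.2 − 8.0 = +1.2, a response. A later 8.4 gives +0.4, not a response.

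**Leverage of one misclassified child on a response rate, 100/n.**

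| n | Source | Points |
|---|---|---|
| 10 | Part D, 6 months to <2 years, minimum (Protocol 3.1.4) | 10.0 |
| 20 | Part C, 4–11 years, minimum (3.1.3); Part D, 2 to <4 years if 30 enrol with 10 younger | 5.0 |
| 30 | Part D total | 3.3 |
| 50 | Part C total | 2.0 |
| 70 | Part C if enlarged | 1.4 |

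**A wider range (assumed).** The documents give no transfusion rate or effect. Suppose 1 to 5 of 30 children are transfused near the visit, with Hb 1 to 2 g/dL higher than it would otherwise be. Take no drug effect and borrow the Part B SD of 0.6.
- Untransfused: P(change >1) = 1 − Φ(1/0.6) = 4.8%.
- Transfused: 50% at +1 g/dL, 95.2% at +2.
- Lowest mix: (29/30)(4.8%) + (1/30)(50%) = 6.3%.
- Highest mix: (25/30)(4.8%) + (5/30)(95.2%) = 19.9%.

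**Mean change (assumed sizes).** Each 10 cm/sec of transfusion-related TCD fall in one child shifts the Part C mean by 10/N: 0.33, 0.20 and 0.14 cm/sec at N=30, 50 and 70. That is 2.2%, 1.3% and 1.0% of the planned 15. Across 1 to 5 of 30 children and falls of 15 to 30 cm/sec, the shift runs from 0.5 to 5.0; no figure in the documents supports the upper end. For Part B, each 1 g/dL in one child shifts the 900 mg mean by 1/12 = 0.083 g/dL at the planned N. At the 25 and 7 participants reported in Protocol 3.5.2 for 900 and 1500 mg, the shifts are 0.040 and 0.143.

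**The case against.** The as-observed approach is legitimate, and for Hb response it is openly stated. That stands, and is why those tables should stay.

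A reader might infer that the other endpoints have no defined analysis. The documents do not support that. The population is everyone dosed, observed values and changes are summarized, nothing is imputed, and no text permits dropping a post-transfusion value. The default is evident; what is missing is the explicit statement that the protocol promised.

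Time to first response might also be read as an omission. It is built from the visit-level responses to which the no-adjustment sentence applies, so it most naturally inherits that rule, although neither SAP says so. Nor is it right that Hb response has no second analysis. It has one, but it does not address transfusion.

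The evidence for on-study transfusion is limited. Protocol 1.1 says that "transfusions are administered to alleviate symptomatic anemia as well as for stroke treatment and prevention", but that is disease background. Section 5.4.1 is an example inside a definition. Section 5.4.7 is the only worked pathway, and it needs two abnormal readings. Transfusion may also do no more than restore Hb toward baseline. All of this stands, and it means that the number affected may be small.

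Part B should not be put on the same footing. Its SAP serves an interim report of a three-part study, so the documents do not show that the sentence in Protocol 10.3.4 existed when it was written.

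Finally, transfusions may appear in the Part C and D concomitant-medication tables by class and preferred name. That could show a total, but those summaries are not tied to a key visit. The SAP texts supplied for Parts C and D contain no table list, and the visible Part B listings may be incomplete, so one cannot say that no output would show the timing.

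**Conclusion.** The point holds for Parts C and D. The Hb response rule, and the as-observed default for normal TCD, can only add favourable outcomes when a transfusion changes a child's classification, and nothing planned in the SAP text shows how often that happens. The size is 3.3 percentage points per misclassified child at n=30, 10.0 in the smallest planned Part D age group, and 2.0 to 1.4 in Part C overall. These are leverage figures, not estimates of bias.

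It would be tempting to conclude that the response rates are materially inflated or that the Part C primary endpoint is compromised. The documents do not support either. They give no transfusion rate, only some transfusions misclassify, one child's effect on mean TCD change is small, and every efficacy summary is descriptive. What is established is a specification gap in a study without a control group, in the direction that favours the drug, with an effect of unknown size.

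**What to change.** Keep the as-observed tables. In the Part C and Part D SAPs:

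1. Add one prespecified companion analysis. A visit within a fixed window after a transfusion, or any visit after chronic or prophylactic transfusion starts, counts as non-response for Hb response, cannot set time to first response and, in Part C, counts as not normal for the TCD proportion.
2. Fix the window before database lock, justify it, and vary it once. The 30 days in Protocol 4.2 is an entry criterion and only a possible starting value.
3. Report the number of children transfused before Week 24 and before Week 48.
4. State that changes in Hb, hemolysis markers and TCD are as-observed. Analyses that exclude post-transfusion values or use the last pre-transfusion value are optional. Exclusion can flatter the mean, because transfused children are likely to be those who worsened.

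For Part B, report the number transfused before Week 24 if it is confirmed that transfusions were captured; the Part A/B SAP does not say so.

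The cost is a derived flag, a few table rows, and possibly slightly lower companion response rates. The Part C and D data are already collected, with one limit. Concomitant-medication recording ends 30 days after the last dose (Protocol 8.4), so later transfusions may be missed in children who stop drug but stay in assessments (6.2).
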